7.3 RECORDING AND REPORTING PROCEDURES

Recording refers to the detection and recording of adverse events; **reporting** refers to the statutory notification by the sponsor to the Medicines and Healthcare products Regulatory Agency (MHRA) and the Main Research Ethics Committee (MREC).

7.3.1 Recording ARs, SARs, SUSARs and other SAEs

All serious adverse events and all adverse reactions will be detected by three procedures:

- The GP or practice nurse records a serious adverse event or an adverse reaction via the online CRF (VIDAL app) as a result of routine clinical contact with the participant.
- Hospital admissions, cancer diagnoses and deaths will be identified automatically through the Hospital Episodes Statistics (HES) system and the NHS Information Centre.
- 3. Hospital admissions for at least one night will also be independently ascertained from all participants except those allocated to open control through their 3-monthly follow-up replies.

In view of the low-risk nature of vitamin D supplementation, only serious adverse events (whether or not causally related, i.e. SAE, SAR or SUSAR) and suspected non-serious adverse reactions (potentially causally related non-serious event, ie AR) will be recorded

by the GP or practice nurse in the safety section of the online CRF (VIDAL app). The criterion for recording an adverse reaction is that there is a reasonable possibility (ie evidence to suggest) that the IMP caused it. Non-serious adverse events deemed unlikely to have a causal relation to the IMP used in this study should not be recorded on the online CRF. Pre-planned hospitalisations (i.e. planned prior to randomisation) and elective treatments of a pre-existing condition do not need to be reported.

Depending on the nature of the reaction or event, the recording and reporting procedures below should be followed. Any questions concerning the reporting of SAEs and ARs should be directed to the Trial Coordinating Centre in the first instance. A flowchart is given in appendix 2 to aid with safety reporting.

7.3.2 Non-serious Adverse Reactions (ARs)

Non-serious adverse reactions (i.e. potentially causally-related adverse events), whether expected or not, should be recorded by the GP practice in the adverse reaction section of the online CRF (VIDAL app). The GP can use the table in section 7.2 above to aid in assessing whether an adverse event should be classed as an adverse reaction: events classed as definitely, probably or possibly related to the IMP should be classed as adverse reactions. The Trial Coordinating Centre will receive automatic notification of all new entries through the online CRF. Non-serious adverse reactions do not require any further reporting.

7.3.3 Serious Adverse Reactions (SARs and SUSARs) and other Serious Adverse Events (SAEs)

All Serious Adverse Events (SAEs), including Serious Adverse Reactions (SARs) and Suspected Unexpected Serious Adverse Reactions (SUSARs), should be recorded in the SAE section of the online CRF (VIDAL app) within 24 hours of the GP practice becoming aware of the event. The Trial Coordinating Centre will inform the Clinical CI of all such notifications.

The online SAE form asks for nature of event, date of onset, severity, corrective therapies given, outcome and causality (i.e. unrelated, unlikely, possible, probably, definitely). Additional information should be added to the online record within 5 days if the event/reaction has not resolved at the time of initial reporting. However, hospitalisations for elective treatment of a pre-existing condition do not need to be reported as SAEs.

SAEs and SARs will be included in the annual development safety update reports (DSURs), but do not require expedited reporting.

7.3.4 Expedited reporting of SUSARs

SUSARs require expedited reporting by the Trial Coordination Centre via the LSHTM study sponsor to the Medicines and Healthcare products Regulatory Agency (MHRA) and the Main Research Ethics Committee (MREC) according to the following timelines:

- (i) Fatal and life-threatening events within 7 days of notification
- (ii) Non-life threatening events within 15 days of notification.

All SUSARs occurring throughout the study will be recorded in the annual DSUR, which will be sent to MHRA, the MREC and the sponsor.

Contact details for reporting SAEs/SARs/SUSARs in the event of failure of the online CRF:

[contact] (Mon to Fri 09.00 – 17.00) E-mail: [contact]

8. ASSESSMENT AND FOLLOW-UP

All study participants allocated to active treatment or placebo will be contacted at least once a month post-randomisation as outlined below. Those on open control will be contacted only at 24 months. The online CRF (VIDAL app) will send weekly reminders to each GP practice, listing all randomised participants with scheduled or overdue quarterly contact. The Trial Coordinating Centre will monitor adverse events, compliance and change of address online and telephone practices to give appropriate reminders.

Automated phone call, e-mail or text message every month from months 1 to 24:

All participants except those randomised to open control (no treatment) will be reminded to take their study medication every month by automated phone call, e-mail or text message generated by the online VIDAL app. No reply will be required from participants.

E-mail or letter follow up at months 3, 6, 9, 12, 15, 18, 21 and 24:

All participants except those randomised to open control (no treatment) will be contacted quarterly by e-mail or post (participant choice of medium) by the GP practice requesting a short reply by the same medium to record the dates on which the last 3 doses of study medication were taken or report reasons for non-compliance, to report any/no planned change of address, and to report any hospital admissions. The 3-monthly follow-up includes a reminder for participants to contact their GP if they are experiencing ongoing symptoms of hypercalcaemia (persistent nausea, vomiting, thirst, passing excessive amounts of urine or feeling generally unwell). All non-responders will be sent one reminder 3 weeks later and then telephoned by the GP practice staff if they have still not replied. Electronic responses will be recorded onto the VIDAL app by participants via a web-link supplied in the e-mail. Postal responses will be entered by the practice nurse on to the VIDAL app, and reminders will automatically be generated for outstanding items.

GP practice visit at month 24:

A repeat blood sample (9 ml lithium heparin vacutainer), blood pressure measurement, and responses to the same lifestyle questions will be obtained 24 months after randomisation for all 1600 participants to quantify differences in vitamin D status (circulating 25(OH)D level) between the intervention and control groups in the blinded and open-label studies.

Each GP practice will also examine all treatment packs brought in at the 2-year visit, cross-checking unused study oil bottles and the study oil dose dates recorded by each participant on the outside of the treatment pack against the compliance information supplied in the quarterly follow-up.

Summaries of GP records for all 1600 participants will also be extracted by the practice staff to obtain unbiased information about GP visits, prescriptions and infections over the preceding 3 years (1 year pre-randomisation and 2 years post-randomisation).

Hypercalcaemia

If a participant reports symptoms of hypercalcaemia during the study, a blood test to check for hypercalcaemia will be performed. If this initial test reveals hypercalcaemia, a repeat test will be performed. If the second test confirms hypercalcaemia, all further doses of IMP will be withheld, and appropriate management of hypercalcaemia will be instituted if necessary. IMP will be discontinued for any participant who develops hypercalcaemia confirmed on two blood tests during participation in the study.

Automated follow-up

All participants will be flagged for lifelong follow-up through national registers for death and cancer registration and tracing by NHS number linkage through the Hospital Episodes Statistics (HES) system for hospital admissions and diagnoses. The logistics of this flagging and linkage will be assessed in the feasibility study, but there will be too few such events for useful analysis in the feasibility study due to limited size and short follow-up.

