6.2 DOSE MODIFICATIONS FOR TOXICITY

6.2.1 Dose modification / reduction / delay

Administration of IMP may be delayed if a participant experiences symptoms of hypercalcaemia, pending investigation (see section 8). Doses of IMP may be administered up to two weeks before or after the scheduled date of administration.

Administration of IMP will be discontinued in the following circumstances:

- 1. If a participant develops hypercalcaemia confirmed on two blood samples as in section 8
- 2. If a participant develops a condition which requires treatment with a prohibited concomitant therapy (see section 4.3)
- 3. If a participant develops a condition which, in the judgement of an investigator, adversely affects that participant's safety, compliance or ability to complete evaluations
- 4. If an investigator concludes that this course of action is in the participant's best interests.

Participants who discontinue the study drug for any reason should not be considered to have withdrawn from the study, and will be invited to attend the practice for the final assessment and blood sample at 24 months.

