APPENDIX 1: SUMMARY OF INVESTIGATIONS, TREATMENT AND ASSESSMENTS

[figure not shown]
| | Visit 1 | Telephone Call | IMP sent | Post or email | Post or email | Post or email | Post or email | IMP sent | Post or email | Post or email | Post or email | Post or email | Visit 2 |
|--|----------|-------------------|--|---------------|---------------|---------------|---------------|----------|---------------|---------------|---------------|---------------|----------|
| | -4 weeks | -1 week | 0 Weeks | Month 3 | Month 6 | Month 9 | Month 12 | Month 12 | Month 15 | Month 18 | Month 21 | Month 24 | Month 24 |
| Sign consent forms | x | | | | | | | | | | | | |
| Eligibility checked | Х | | | | | | | | | | | | |
| Give personal/medical details | Х | | | | | | | | | | | | х |
| Complete online CRF | Х | | | | | | | | | | | | х |
| Blood pressure, waist circumference, height and weight measured | х | | | | | | | | | | | | х |
| Give blood sample | Х | | | | | | | | | | | | х |
| Confirm eligibility and willingness to be randomised | | х | | | | | | | | | | | |
| Randomisation, IMP sent, (unless open control), medication receipt confirmed | | | х | | | | | х | | | | | |
| Monthly reminder to take study medication | | | Automated phone call, e-mail or text every month from month 1 - 24 to remind participants to take their study medication | | | | | | | | | | |
| Take study medication | | | Study medication taken every month from when it is received at week 0 and month 12 (24 times in total) | | | | | | | | | | |
| Confirm medication taken | | | x | | | | | | | | | | |

VIDAL Trial Protocol Page 43 of 45 Version 3, 25.07.2012

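### The automated monthly dosing reminder excepts only open control, so as worded it also goes to participants whose study oil has been stopped or put on hold on medical grounds

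*Protocol*

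**What the plan says.** **The reminder.** Section 8 states: "All participants except those randomised to open control (no treatment) will be reminded to take their study medication every month by automated phone call", or by e-mail or text. It adds: "No reply will be required from participants". The opening of section 8 likewise sets monthly contact by allocated arm, not by whether the person is still taking the oil. The reminder row of Appendix 1 reads: "Automated phone call, e-mail or text every month from month 1 - 24 to remind participants to take their study medication". It makes no exception for oil that has been stopped or held.

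**Holding and stopping.** Section 6.2.1 allows a temporary hold: "Administration of IMP may be delayed if a participant experiences symptoms of hypercalcaemia, pending investigation". It requires discontinuation in four circumstances: hypercalcaemia confirmed on two samples; "If a participant develops a condition which requires treatment with a prohibited concomitant therapy"; a condition that an investigator judges to affect safety, compliance or evaluation; and an investigator's conclusion that stopping is in the participant's best interests. Section 8 repeats the rule for hypercalcaemia: "If the second test confirms hypercalcaemia, all further doses of IMP will be withheld". Separately, section 4.4 allows interruption or stopping by the participant's choice or at the GP's discretion.

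**Status afterwards.** Section 6.2.1: "Participants who discontinue the study drug for any reason should not be considered to have withdrawn from the study". They are still invited to the 24-month visit.

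**Where the oil is.** Packs of 12 bottles are posted to the home (6.1.3, 6.5.2), and participants are asked to keep both packs until the final visit (5.1.5). No earlier collection is described.

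**The concern.** The monthly message is a direct instruction to dose, sent to a person who holds the bottles. For someone told to stop or wait because of suspected or confirmed hypercalcaemia, or because a prohibited drug has been started, it contradicts the clinician's instruction. The message asks for no answer, so the message itself gives no occasion to find the mistake. The stake is participant safety in a small number of people and consistency between two rules of the same protocol. For a placebo recipient the message is only a nuisance.

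**Working it through.** The point is one of wording, so the check is to set the rules side by side. A little arithmetic shows scale.

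**Step 1. Who receives the reminder.** Section 9.1 plans 1,600 participants, 400 of them open controls. The rule therefore covers 1,600 − 400 = 1,200 people, of whom 400 + 400 = 800 are on vitamin D and 400 on placebo.

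**Step 2. Does a medical hold or stop take someone out of that group?**
- Symptoms under investigation: the dose may be delayed (6.2.1). The person is still allocated to oil and still in the study, so the reminder applies.
- Confirmed hypercalcaemia: further doses are withheld (section 8) and the oil is discontinued (6.2.1). The person has not withdrawn, so the reminder applies.
- Prohibited therapy now needed, or investigator judgement: the oil is discontinued (6.2.1). The person has not withdrawn, so the reminder applies.

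**Step 3. Is there a switch-off elsewhere?** The reminder appears in 5.1.1, section 8 and Appendix 1. Stopping and withdrawal appear in 4.4, 6.2.1, section 8 and 11.3. None of these suspends the message.

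**Step 4. Scale per person (illustration only).** With one reminder per dose over months 1 to 24, a stop after dose k leaves about 24 − k reminders. Bottles at home number 12 − k before the second pack and 24 − k after it. Each bottle is 100,000 IU on vitamin D and 0 IU on placebo.

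| Stop after dose | Reminders left | Bottles at home | Stock if on vitamin D |
|---|---|---|---|
| 3 | 24 − 3 = 21 | 12 − 3 = 9 | 900,000 IU |
| 11 | 24 − 11 = 13 | 12 − 11 = 1 | 100,000 IU |
| 18 | 24 − 18 = 6 | 24 − 18 = 6 | 600,000 IU |

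The last column is an upper bound on what that stock could deliver, not an expected exposure.

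For a hold of d days starting at random in a 30.4-day month, the chance that a reminder falls inside it is min(1, d/30.4). The protocol gives no duration. Assuming 7 days gives 7/30.4 = 23%, 14 days gives 14/30.4 = 46%, and a month or more gives 100%. These figures only restate the assumed durations.

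**Step 5. Cost of silencing the reminder for a time.** Section 3.1.1 counts a vitamin D participant as compliant with at least 19 of 24 doses and attendance at the 2-year visit. Up to 24 − 19 = 5 missed doses therefore do not by themselves make a participant non-compliant. A short hold may cost no dose at all, since section 6.2.1 says: "Doses of IMP may be administered up to two weeks before or after the scheduled date of administration".

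**The case against.** **The sentence only describes the planned course.** Appendix 1 also shows 24 doses taken, and no one reads that as overriding 6.2.1. This has some force. But section 8 names who is excepted and names one group, and a system that runs the rule as written will send the message.

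**The app may already suppress it.** The Trial Coordinating Centre defines the app's specification outside the protocol (section 12), and the trial has standard operating procedures that are not shown. A reader might infer that messages will in fact go to people with hypercalcaemia. The protocol cannot show that. It shows only that the written rule would send them and that nothing in the document prevents it.

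**Other controls exist.** These stand and reduce the risk. The GP gives the instruction to stop. The quarterly contact asks for dose dates or reasons for non-compliance, restates the symptoms of hypercalcaemia and is followed by a reminder and a telephone call (section 8). The Centre monitors adverse events and compliance online (section 8, 10.2) and is notified automatically of adverse reactions entered by practices (7.3.2). None of them turns the reminder off.

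**The IU figures look alarming.** A reader might take 900,000 IU as the likely overdose. It is cupboard stock. Taking it would mean nine successive doses against medical advice, across about three quarterly contacts.

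**Stopping all reminders could harm the trial.** This also stands. Compliance is a primary outcome, and a reminder may bring back someone who has lapsed by choice. The exception should therefore cover medical stops and holds only.

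**The year-2 pack.** Sections 5.1.5 and 6.1.3 also go by allocation, and a reader might infer that a second pack would reach a participant with hypercalcaemia. That is unlikely: a clinician signs the prescription (5.1.5), and hypercalcaemia is to be reported to the Centre (3.3).

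**Conclusion.** The point holds as a cheap improvement. The written reminder rule conflicts with the instruction to hold or discontinue the oil on medical grounds, and no other section resolves the conflict. The conclusion rests on the text alone: one stated exception, participants who stop staying in the study, and bottles kept at home.

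The practical size is small and cannot be counted. The protocol gives no rate of stops or holds and calls vitamin D hypersensitivity very rare (3.3). Stops for prohibited therapy or investigator judgement add to these, also without a stated rate. The documents do not support a claim of expected harm or of an effect on sample size, randomisation or analysis.

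**What to change.** In section 8 and in the reminder row of Appendix 1, also except participants whose oil has been discontinued or put on hold by the GP or an investigator under 6.2.1 or section 8. The exception runs from the date the practice records this in the VIDAL app until it records resumption, with the existing two-week dosing window applying. Show open holds in the weekly list that the app already sends to practices, so that none is forgotten.

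Participants who lapse by their own choice keep receiving reminders unless they ask for them to stop. Quarterly follow-up and the month-24 visit continue for everyone who now receives them. The events that hold or stop treatment stay as they are.

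Optionally, 5.1.5 and 6.1.3 could say that the second pack is issued only to participants not under a medical stop or hold, checked when the prescription is signed.

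The cost is an exception phrase in two places, a status field for practices to maintain, and an extra item in the weekly list. The downside is that reminders may restart late if resumption is entered late, which could cost a dose or more.

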8.1 LOSS TO FOLLOW-UP

We expect the level of loss to follow-up (failure to contact non-responders by post or telephone) to be low. All participants will be consented at enrolment for flagging for lifelong follow-up through national registers for death and cancer registration and tracing by NHS number linkage through the Hospital Episodes Statistics (HES) system for hospital admissions and diagnoses.

8.2 TRIAL CLOSURE

The end of the study will be defined as the date of the final study visit of the final participant undergoing follow-up.

9. STATISTICS AND DATA ANALYSIS

All data required for analysing compliance and outcomes will be available from the online CRF (VIDAL app), together with the 25(OH)D results on the baseline and 2-year blood samples, and data extracted from GP notes or reported through flagging for hospital admissions (HES), cancer incidence and mortality.

9.1 SAMPLE SIZE

We will recruit 1,600 participants aged 65-84 through 20 GP practices (400 on open label vitamin D v. 400 open controls; 400 blinded to vitamin D v. 400 placebo). Our target is to randomise an average of 80 participants aged 65-84 per GP practice (at least 9% participation rate). It will be clear within the first six months if recruitment in some practices is falling well below this target. If this occurs, recruitment in other practices will continue after 80 participants have been randomized to achieve the overall target of 1,600 participants.

9.2 POWER

The main purpose of the feasibility study is to pilot the organisational procedures for the main trial, to demonstrate adequate recruitment, and to prepare us for any unexpected difficulties in running it. All eligible patients in each practice will therefore be invited, as would be required in the main trial. In addition, the number of practices involved must be large enough for them to be representative of the diversity of practices that may participate in the main trial, so that average recruitment (the proportion of those invited who are randomized) is a reliable estimate of what would be achieved in the main trial.

The proposed feasibility study (10 practices with placebo control and 10 with open control, with 80 participants per practice) also has adequate power to show a difference in recruitment depending on the design (open-label v. blinded).

The plan is to make comparisons between blinded and open control designs in 10 pairs of practices matched on distribution of socio-economic status, with a nominal two-sided alpha-level of 5%. Each practice will recruit approximately 80 participants. To estimate the power we simulated the number of patients that one would need to approach in each practice in order to recruit 80 participants (negative-binomial). We assumed the design would change the mean participation rate from 10% (range 2.5% to 17.5%) to 15% (5.7% to 24.3%). Under these assumptions the power to detect this difference would be 92%. (If there were no heterogeneity between practices, the overall recruitment rate would be estimated very precisely, e.g. 9% with standard error 0.2%.)

Additionally, to detect a difference of 10% in any binary outcome the trial will have (at least) 80% power (using a nominal 5% significance level) for any within practice comparison such as vitamin D v. placebo (400 per arm), and 70% power for any between practice comparison such as placebo v. open control (sign test with 10 pairs of practices; power = 70% for 0.45 v. 0.55, and 88% for 0.10 v. 0.20). The outcome might be reporting a respiratory infection (15% versus 25%) or compliance (85% versus 95%).

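### The 70% and 88% power in Section 9.2 is not reached for placebo v. open control: a two-sided 5% sign test on 10 pairs, 40 per practice, gives 42-48% and 72-79% at best

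*Protocol*

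**What the plan says.** Section 9.2 (Power) introduces the comparisons of blinded and open designs in 10 matched pairs of practices "with a nominal two-sided alpha-level of 5" per cent. After the recruitment calculation (92% power) it turns to other binary outcomes with a 10-point difference, again "using a nominal 5% significance level". For comparisons within practices it claims at least 80% power with 400 per arm. For comparisons between practices it claims "70% power for any between practice comparison such as placebo v. open control (sign test with 10 pairs of practices"), with the detail "sign test with 10 pairs of practices; power = 70% for 0.45 v. 0.55, and 88% for 0.10 v. 0.20". Its two example outcomes are respiratory infection, 15% v. 25%, and compliance, 85% v. 95%.

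The group sizes are in Section 9.1: "400 on open label vitamin D v. 400 open controls; 400 blinded to vitamin D v. 400 placebo". Section 9.2 confirms "10 practices with placebo control and 10 with open control, with 80 participants per practice", and Section 5.1.5 sets 1:1 allocation within each practice. Section 9.3.1 describes the main analysis only as a matched-pair comparison of recruitment and overall compliance. It names no test.

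**The concern.** The sign test is coarse with 10 pairs. Its attainable levels jump from 2.1% (9 of 10) to 10.9% (8 of 10), so a nominal 5% test really runs at 2.1%. With only 40 participants per practice in each arm, chance alone reverses or ties a fair share of pairs even when the true difference is 10 points. The stated 70% and 88% look too high for that test at that size.

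Placebo v. open control is one of the reasons for having two designs. Section 2.1 makes contamination in placebo and open controls part of the primary objective, and Section 1.2 lists the reliability of self-reported infections among the questions for the cluster comparison. If power is below one half where 70% is claimed, a null result could be read as evidence that the open design does no harm, and carried into the choice of design for the 20,000-person main trial.

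**Working it through.** **Inputs.** 10 pairs, sign test and two-sided 5% (Section 9.2); 400 placebo and 400 open controls (Section 9.1); 10 practices per design (Section 9.2). Per practice and arm: 400 / 10 = 40. Whole design: 800 / 10 = 80.

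**Check on the neighbouring figure.** A two-sample comparison of 0.45 v. 0.55 with 400 per arm has power 0.809, which agrees with the stated 80%. The within-practice claim is sound.

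**Critical value.** With 10 untied pairs under the null:
- 9 or more in one direction: 2 × (10 + 1)/1024 = 0.021
- 8 or more: 2 × (45 + 10 + 1)/1024 = 0.109

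So the two-sided 5% test needs at least 9 of 10.

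**Outcome of one pair.** Exact probabilities from two independent binomials with n = 40 and no variation in the true rates between practices:

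| Rates | Expected direction | Tie | Opposite |
|---|---|---|---|
| 0.45 v. 0.55 | 0.785 | 0.059 | 0.156 |
| 0.10 v. 0.20 | 0.867 | 0.057 | 0.075 |

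**Power, ties split.** With q = P(expected direction) + P(tie)/2, power = 10q⁹(1 − q) + q¹⁰.
- 0.45 v. 0.55: q = 0.814, power = 0.292 + 0.128 = 0.42
- 0.10 v. 0.20: q = 0.896, power = 0.387 + 0.333 = 0.72

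**Power, ties dropped.** The number of untied pairs is binomial, and the exact two-sided 5% critical value is used for each number. Power is 0.479 and 0.790.

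**All cases on the same two tie conventions (split to dropped), no practice variation:**

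| Rates | Stated | 40 v. 40 | 80 v. 80 |
|---|---|---|---|
| 0.45 v. 0.55 | 70% | 42-48% | 73-77% |
| 0.10 v. 0.20 | 88% | 72-79% | 95-97% |
| 15% v. 25% | at least 70%, as a 10-point difference | 61-69% | not needed here |
| 85% v. 95% | at least 70%, as a 10-point difference | 87-92% | 99% or more |

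**Attempts to reproduce 70% and 88% together.**
- One-sided 5%, ties dropped, 40 v. 40: 52% and 82%. Eight of 10 has one-sided p = 0.055, so with 10 untied pairs the threshold is still 9.
- Rejecting at 8 of 10, ties split, 40 v. 40: 72% and 92%, but at a two-sided level of 10.9%.
- 80 v. 80: 73-77% and 95-97%. The first figure is met, but the second is not 88%.
- 80 per practice with an unstated practice SD of 2.5 points: 64-69% and 86-90%. This comes close, but the SD is not in the protocol and the size is not that of the named comparison.

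**Effect of practice variation.** Section 9.2 gives no SD for these outcomes. Assuming an SD of the true practice rates of 3 to 5 points (beta-binomial), sign-test power at 40 per practice falls as follows:
- SD 3 points: 37-42% and 61-68%
- SD 5 points: 31-35% and 48-55%

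**Paired t-test on the 10 differences, 40 per practice.** Noncentrality = 0.10 / √(V/10) on 9 degrees of freedom, with V = [p₁(1 − p₁) + p₂(1 − p₂)]/40 + 2·SD².
- SD 0, 0.45 v. 0.55: V = 0.495/40 = 0.0124, noncentrality 2.84, power 72%
- SD 0, 0.10 v. 0.20: V = 0.25/40 = 0.00625, noncentrality 4.00, power 94%
- SD 3 to 5 points: 66% down to 57%, and 88% down to 76%

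**The case against.** The strongest reply is that the comparison named in Section 9.3.1, overall compliance by design, uses whole practices of about 80, where the sign test has 73-77% and 95-97% without practice variation. There the 70% is met. Neither example outcome lies near 50%, where the shortfall is worst: 85% v. 95% keeps 87-92% even at 40 per practice, and 15% v. 25% falls only modestly short at 61-69%. All of that stands. It does not rescue the sentence, which names two single arms just after speaking of 400 per arm and extends the claim to any between-practice comparison.

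A reader might infer that all the blinded v. open comparisons, overall compliance included, are badly underpowered. The figures above do not support that. A reader might also infer that the protocol assumed identical true rates in all practices. It does not say so: Section 9.2 states no variance assumption for these outcomes, and its recruitment calculation does model heterogeneity. Zero variation is used here only as the most favourable case.

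It is fair, too, that the sign test is valid though conservative, that it appears only in the power statement, and that the analysis test may be fixed in a statistical analysis plan not seen here. The error is in the stated power, and replacing the test is a preference. Finally, this is a feasibility study. The power figure is introduced as an addition, does not set the sample size, and leaves the recruitment power untouched.

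**Conclusion.** The point holds for arm-level comparisons between practices. For placebo v. open control, the comparison Section 9.2 names, the sign test delivers 42-48% where 70% is stated and 72-79% where 88% is stated. The chance of missing a true 10-point difference at 0.45 v. 0.55 is therefore 52-58%, not 30%. At 15% v. 25% it is 31-39%.

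This rests on 40 participants per practice and arm (from Sections 9.1 and 5.1.5), the two-sided 5% level, 10 pairs, and no practice variation; any variation makes it worse. The range within each figure is the treatment of ties. The 3 to 5 point practice SD is an assumption made here, and the conclusion does not depend on it.

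**What to change.** In Section 9.2:

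1. Replace 70% and 88% with the power for 40 per practice: 42-48% and 72-79% if the sign test is kept, naming the tie rule.
2. Remove the word that extends the claim to every between-practice comparison, or give arm-level (40 per practice) and whole-design (80 per practice, 73-77% and 95-97%) power separately.
3. State the between-practice variation assumed for these outcomes.
4. Preferably, base the power and the matched-pair comparison on a paired t-test of the 10 within-pair differences: about 72% and 94% at 40 per practice with no practice variation. Show 57-66% and 76-88% as a sensitivity range, labelled as resting on an assumed practice SD of 3-5 points. This is compatible with Section 9.3.1.

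The cost is wording only, with no change to recruitment or conduct. The stated power becomes less favourable once practice variation is admitted, and the t-test relies on 10 differences being roughly normal.
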